- Continuity in readings of fetal heart rate (as measured in the number of minutes without a readable tracing in a 30 minute sample tracing) between EUM and fetal scalp electrode and external fetal heart rate monitoring from the same patient
- Continuity in readings of contractions (as measured in the number of minutes without a readable tracing in a 30 minute sample tracing) between EUM, IUPC and external tocodynamometer from the same patient

Secondary Outcomes:

- Compare average frequency of contractions between the monitoring systems
- Compare duration of contraction between the monitoring systems
- Compare maximum height of the contraction between the monitoring systems
- Compare total Montevideo units obtained between the monitoring systems
- Compare the timing of the contraction between the monitoring systems
- Compare average fetal heart rate between the monitoring systems
- Compare baseline heart rate between the monitoring systems
- Compare the number accelerations between the monitoring systems
- Compare the number of decelerations between the monitoring systems
- Compare the timing of the accelerations between the monitoring systems
- Compare the timing of decelerations between the monitoring systems
- Compare the maximum fetal heart rate achieved during acceleration between the monitoring systems
- Compare the lowest fetal heart rate achieved during deceleration between the monitoring systems
- Compare the degree of variability in the tracing between the monitoring systems. Degree of variability will be defined as the correlation between the tracings. The tracings will be broken down into 4 minute intervals and defined as minimal, moderate or marked variability and compared with each other for accuracy and

Version 5.13; June 19, 2020

consistency. Most accurate will be the internal monitor in each case, i.e. fetal scalp electrode.

- Compare patient satisfaction between the monitoring systems

Inclusion criteria:

- 1) Maternal age >18 years old
- 2) Singleton pregnancy
- 3) Gestational age of 24 completed weeks or greater based on the estimated due date as calculated from last menstrual period or early ultrasound
- 4) Category I (reassuring) fetal heart rate tracing at time of enrollment

Exclusion criteria:

- 1) Fetal anomaly or chromosome defect
- 2) Allergy to silver
- 3) Woman with implanted electronic device of any kind
- 4) Irritated skin or open wound on the abdominal wall

Recruitment Mechanisms:

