#### Device Description:

The EUM300 is composed of three units: Disposable electrode, Maternal unit and Interface unit.

Disposable electrode applied part – Proprietary bio-compatible patch electrode array with nine Ag/AgCl and hydrogel connections. Electrode is made by US based manufacturers: Lead-Lok, Sandpoint, ID and Molex, Naperville, IL.

Maternal Unit – The maternal unit is connected via a proprietary connector to the electrode. The EMG signals are amplified by an analog front-end. OB-Tools Algorithm runs on a DSP board and the result – Fetal Heart Rate and Uterine Activity are transmitted via Bluetooth. The unit contains a 4.2V Li-Ion rechargeable battery. The battery allows 24h of work and must be charged away from the patient.

Interface unit – Wall mount unit translates the information received from a paired Bluetooth Maternal unit. In this setup the EUM is used as a secondary system, one that

Version 5.13; June 19, 2020

is not involved with clinical decisions. In this case a PC computer receives the bluetooth transmission from the maternal unit and saves it into an Excel readable file. A primary monitor that is used for clinical decisions may also be connected to the PC and its data is recorded into the same file for comparison. The file format is a simple 6 column format: Date, Time, EUM UA, EUM FHR, Monitor UA, Monitor FHR. The file can be read and analyzed using Excel, Matlab and other statistical tools.

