Because many of these patients will overlap due to the fact that they will serve as their own control and will be monitored simultaneously for fetal heart rate and change in cervical exam, it is anticipated that the maximum number of patients required in this study will not be more than 220 patients since 55 obese and 55 non-obese patients will be needed and additional patients may be needed to evaluate productive contractions. In addition to comparing the continuity in readings, in assessing contractions, we will also compare average frequency of contractions, the duration of contraction, maximum height of the contraction, the total Montevideo units obtained, the timing of the contraction and the amount of discontinuous tracings from the devices. In assessing fetal heart rate, we will compare average fetal heart rate, baseline heart rate, the number accelerations, the number of decelerations, the timing of the accelerations, the timing of decelerations, the maximum fetal heart rate achieved during acceleration, the lowest fetal heart rate achieved during deceleration, and compare the degree of variability in the tracing. A continuous outcome will be compared using a paired t-test.

Version 5.13; June 19, 2020

As each patient is serving as its own control, missing data is unlikely to be an issue in this study once the patient consents. If the monitoring is less than 30 minutes, these patients will not be used in analysis due to concern for completeness and accuracy.

Safety assessment:

Safety and tolerability will be assessed by recording of adverse events. Adverse events will be reported. Adverse events will be assessed in terms of their seriousness, severity, and relationship to the study device. To date more than 800 patients have used the device in clinical trials and there have been no safety events reported with the use of the device to date.

Potential benefits:

There is no immediate benefit to the subject from her participation in this study. The study results will support the development of the EUM300pro system, which may have clinical importance in providing the care provider with more continuous and accurate monitoring of fetal heart rate and contractions in a less invasive way. These parameters will aid the medical staff in making timely clinical decisions and increasing the chances of attaining a successful treatment and/or delivery.

Potential risks:

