### Option 2 - EUM300 with dedicated notebook

The proposed setup eliminates the need to install the interface unit during the clinical evaluation time frame and minimize the required changes to the delivery room setup. The maternal unit will transmit the uterine activity/fetal heart rate information to an off-the-shelf computer equipped with Bluetooth V4.0 (e.g., Lenovo IdeaPad U41-70). An existing fetal monitor transmits similar information using HP-50 protocol over RS232 physical connection. The RS232 is likely to be connected to existing hospital IT. A simple Y connection is the only change needed to the delivery room. The RS232 transmissions will also be received by an off-the-shelf USB-RS232 adaptor.

Version 5.13; June 19, 2020

---

A computer program will record both the EUM300 and the fetal monitor into a common file (CSV format in order to be able to be analyzed by either Matlab or Excel). Program may also present the four signals (EUM Uterine, EUM FHR, monitor Uterine, monitor FHR) in real time. Other features may be: Dialog to provide the file information with patient ID, name, gestational age, etc.

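### Event timing is compared across two recording chains with no stated time-stamp source or delay check, so a recording offset could not be told apart from a device timing difference

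*Combined protocol and SAP*

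**What the plan says.** The Secondary Outcomes list (under Materials and Methods) includes "Compare the timing of the contraction between the monitoring systems", "Compare the timing of the accelerations between the monitoring systems" and "Compare the timing of decelerations between the monitoring systems". The Objectives and Statistics sections repeat these comparisons. None of them defines the event point (onset, peak or end), the rule for pairing events, or a tolerance.

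The Device Description says that "OB-Tools Algorithm runs on a DSP board" in the maternal unit, with Bluetooth transmission after that. Of the clinical monitor it says "its data is recorded into the same file for comparison". The file layout is given in full: "The file format is a simple 6 column format: Date, Time, EUM UA, EUM FHR, Monitor UA, Monitor FHR". The section on Option 2 describes the monitor's route (HP-50 protocol over RS232, received through a USB adaptor) and adds: "A computer program will record both the EUM300 and the fetal monitor into a common file".

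For the analysis, Statistics says "A continuous outcome will be compared using a paired t-test". It also mentions routine parametric and non-parametric methods in general terms.

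**The concern.** Four signals share one Date and Time pair, and they arrive by two routes with different processing and transmission steps. If one route is slower and the file does not correct for it, every event on that route appears late by the same amount. Using each woman as her own control does not help, because the offset has the same sign in every woman and stays in the paired difference.

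A paired t-test on timing asks only whether the mean difference is zero. That confounds recording offset with device error, and it says nothing about scatter: two devices could disagree widely event by event and still average to zero. A significant result could be read as the EUM mistiming events when part or all of it is recording delay. A non-significant result would be just as hard to read. Since the study's stated purpose is to validate the EUM's accuracy, these outcomes should be interpretable.

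**Working it through.** The plan states no delay, tolerance, SD or sample size for timing, so there is no figure of its own to reproduce. The calculation below is illustrative.

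**Inputs from the plan (Statistics).** n = 39 for the heart-rate comparisons; n = 55 in each BMI group for the contraction comparisons; alpha 0.05. Two-sided testing is stated for the McNemar comparison and assumed here for timing.

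**Assumptions.** The true timing difference is zero. The net recording offset b is 0.5 to 3 s. The SD s of each woman's mean timing difference is 3 to 20 s.

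**Bias.** If the observed difference is D = true difference + b + error, then E(D) = 0 + b. The bias equals b, whatever the SD or n.

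**Probability of a significant result.** With T noncentral t on n − 1 degrees of freedom and noncentrality λ = √n × b / s, the rejection probability is P(|T| > t), where t is the 0.975 quantile of central t. That quantile is 2.024 for n = 39 and 2.005 for n = 55. Two examples at n = 39:

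- b = 2, s = 3: λ = 6.245 × 2/3 = 4.16, probability 0.98.
- b = 0.5, s = 5: λ = 6.245 × 0.5/5 = 0.62, probability 0.09. The case b = 2, s = 20 has the same λ and the same result.

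| SD (s) | n | b = 0.5 s | 1 s | 2 s | 3 s |
|---|---|---|---|---|---|
| 3 | 39 | 0.17 | 0.53 | 0.98 | 1.00 |
| 5 | 39 | 0.09 | 0.23 | 0.68 | 0.96 |
| 10 | 39 | 0.06 | 0.09 | 0.23 | 0.45 |
| 20 | 39 | 0.05 | 0.06 | 0.09 | 0.15 |
| 3 | 55 | 0.23 | 0.68 | 1.00 | 1.00 |
| 5 | 55 | 0.11 | 0.31 | 0.83 | 0.99 |
| 10 | 55 | 0.06 | 0.11 | 0.31 | 0.59 |
| 20 | 55 | 0.05 | 0.06 | 0.11 | 0.19 |

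Put without units, rejection reaches 80% when b/s is 0.46 at n = 39 and 0.39 at n = 55.

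**Correlation of tracings.** The secondary outcomes define degree of variability as a correlation between tracings, but do not say how it is computed. If it were sample by sample, a pure sinusoid of period P and its copy lagged by L would correlate at cos(2πL/P). For L = 3 s this is 0.31 (P = 15 s), 0.59 (P = 20 s) and 0.95 (P = 60 s). For L = 1 s it is 0.91 (P = 15 s) and 0.95 (P = 20 s). The periods are assumptions, and real tracings are not pure sinusoids. The same outcome also grades variability over 4-minute intervals; 3 s is 3/240 = 1.25% of an interval, so those grades would hardly change.

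**The case against.** A reader might infer that events are stamped on arrival at the computer, that the two chains have unequal delays, and that a false timing difference will therefore be reported. The documents do not support this. They show one Time column but do not say who assigns the stamp or whether the program aligns the streams. They give no latency for either chain. Nor is it true that any constant delay makes the test reject: several cells in the table sit close to 5%.

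Four further points have weight. First, the plan does not say whether timing will be taken from the file or scored by a reader, so a t-test on raw file times is not certain. However, Materials and Methods says that both systems' data are captured on the study laptop for comparison, so an offset there would carry into readings made from that record. Second, some delay belongs to the device: the Introduction says Doppler averages the last three beats, and that is part of how Doppler performs. Third, the EUM measures electrical activity, while the tocodynamometer and pressure catheter measure mechanical effects. A constant lag may therefore be real, and simply subtracting it would erase a finding. This stands, and it is why raw results must be shown beside aligned ones. Fourth, the scope is limited: three of fifteen secondary outcomes, with variability arguable as a fourth.

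What remains is the absence of any provision for telling these sources apart, together with a test that cannot do so.

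**Conclusion.** The concern holds as a gap in the plan's ability to interpret timing, not as a demonstrated error in the results. Different chains, one Time column and no synchronisation or delay check mean that a net recording offset, if present, biases the mean timing difference by its full size and cannot be separated from a device difference.

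The consequence for significance ranges from near the nominal 5% to near certainty, and it rests entirely on assumed offsets and SDs. A loss of tracing correlation is possible only if the correlation is computed sample by sample, and its size depends on signal frequency. The 4-minute variability grades and the primary outcomes, which count unreadable minutes, are essentially unaffected. The change is worth making because an agreement analysis answers the timing question better than a test of zero mean difference, and it is cheap.

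**What to change.** Replace the paired t-test for timing with an agreement analysis, prespecified as follows:

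1. State how the file's time stamps are assigned.
2. Define the event point for contractions, accelerations and decelerations, and match events between systems within a fixed window.
3. On the raw file times, report the mean timing difference (the offset) and limits of agreement.
4. As a second analysis, estimate one offset per recording by cross-correlation, separately for the uterine-activity and heart-rate channels. Report the distribution of these offsets, then give limits of agreement and any tracing correlation after alignment. Show raw and aligned results side by side, since alignment also removes real between-woman differences in offset.
5. State that a constant offset will not be interpreted as EUM mistiming, because chain delay, device processing and a true electrical-versus-mechanical lag cannot be told apart from these data.

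The cost is a short script and one paragraph in the Statistics section. The price is that no formal claim can be made about a constant timing difference between devices.

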**Introduction:**

Monitoring of fetal heart rate and uterine contractions are crucial to determining fetal well-being and labor progress. The current methods available for monitoring fetal heart rate and contraction frequency and intensity are either externally applied (i.e. Doppler ultrasound for determining the fetal heart rate and tocodynamometry for measuring contractions) or require invasive insertion in the presence of cervical dilation and rupture of membranes (i.e. fetal scalp electrode for determining fetal heart rate and intrauterine pressure catheter for measuring contractions). While the invasive devices represent the

Version 5.13; June 19, 2020

“gold standard” for monitoring, their invasive nature comes with limitations of when they can be used and has risks of infection, etc.i

The noninvasive devices have limitations in their accuracy. Although the tocodynamometer is noninvasive, it can only be used to measure contraction frequency. Additionally, it is difficult to obtain an accurate tracing in patients that are obese or in pain and unable to lie still. The fetal Doppler averages the last three beats, which limits its accuracy. Both are limited in that maintaining proper placement on the maternal abdomen is limited in the presence of both maternal and fetal movement.

Obesity during pregnancy presents significant challenges to monitoring uterine activity and fetal heart rates with the usual external devices. The tocodynamometer works by through a button on the underside of the device that is pressed when the uterus becomes firm and moves anteriorly in the maternal abdomen during a contraction. The ability of the uterus to “push” this button becomes more limited the greater the amount of adipose tissue interposed between it and the button. Additionally, with obesity keeping the tocodynamometer and the Doppler ultrasound device (used to monitor the fetal heart rate noninvasively) in their proper positions in order to obtain useable tracing becomes a significant obstacle.

For these reasons developing a device that is noninvasive but has similar accuracy to a fetal scalp electrode and an intrauterine pressure catheter is of paramount importance.

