#### Objectives:

Version 5.13; June 19, 2020

1. Compare the contraction tracings obtained using the EUM device vs. those obtained using the intrauterine pressure catheter vs. those obtained from external tocodynamometer among current obese patients (BMI greater than 30 kg/m^2) and nonobese patients using simultaneously obtained, 30 minute tracings with regards to the frequency of contractions, the duration of contractions, maximum height of the contractions, the total Montevideo units recorded, the timing of the contractions, and the amount of discontinuous tracings from the devices. Of the variables mentioned, the Montevideo units will only be comparable between the IUPC tracings and the EUM device.
2. Compare the fetal heart rate tracing obtained via the EUM device vs. external fetal Doppler vs. fetal scalp electrode (simultaneously obtained, 30 minute tracings will be compared) among obese patients and nonobese patients with regards to the amount of discontinuous/uninterpretable tracing, average fetal heart rate, baseline heart rate, the number accelerations, the number of decelerations, the timing of the accelerations, the timing of decelerations, the maximum fetal heart rate achieved during acceleration, the lowest fetal heart rate achieved during deceleration, and compare the degree of variability in the tracing.
3. Compare tracings of productive vs. non-productive contractions in patients presenting to triage to rule out labor (30 minutes of simultaneously obtained tracings of external tocodynamometer and EUM device will be compared) with regards to the frequency of contractions, the duration of contractions, maximum height of contractions, the timing of the contractions and the amount of discontinuous tracings from both devices, as well as changes in cervical exam on the basis of body mass index. Productive contractions are those that cause a change in cervical exam of 1 cm or more, any change in station or change in effacement of 50% or more.

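### Fetal heart rate variability has two non-equivalent definitions, and the one labelled as the definition, a correlation, does not measure variability

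*Combined protocol and SAP*

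**What the plan says.** Objective 2 sets out to "compare the degree of variability in the tracing" across the EUM, the external Doppler and the fetal scalp electrode (FSE), alongside other heart rate features. It specifies that "simultaneously obtained, 30 minute tracings will be compared".

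The outcome is made operational in the Secondary Outcomes list under Materials and Methods. One bullet contains three statements:

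- A definition, which rests on a pair of devices: "Degree of variability will be defined as the correlation between the tracings".
- A classification, which rests on single intervals: "The tracings will be broken down into 4 minute intervals and defined as minimal, moderate or marked variability", after which the classes are compared to judge how accurate and consistent they are.
- A choice of reference device: "Most accurate will be the internal monitor in each case, i.e. fetal scalp electrode".

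No type of correlation, sampling interval, class cut-points or agreement statistic is given. The Statistics section lists variability again among the heart rate comparisons and adds only that "A continuous outcome will be compared using a paired t-test".

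Two other places matter. The Introduction says of the current external method: "The fetal Doppler averages the last three beats, which limits its accuracy". The Device Description lists the columns of the recorded file as "Date, Time, EUM UA, EUM FHR, Monitor UA, Monitor FHR", so there is one EUM heart rate signal and one conventional-monitor heart rate signal. The dedicated-notebook set-up (Option 2) names the same four signals.

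**The concern.** The bullet gives one outcome two definitions that are not interchangeable. A correlation belongs to a pair of tracings. A class belongs to one interval of one tracing. Two analysts could each follow the text and report different endpoints.

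The sentence that uses the word for a definition is also the one that does not fit the objective. Comparing the degree of variability between devices needs a value for each device, and a correlation supplies none. The paired t-test cannot be applied to it either, because there are no two device values to pair.

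This matters here because the protocol itself names averaging as a limit on Doppler accuracy. Variability is an outcome where averaging could show, and a correlation can stay high while short-term variation is lost.

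**Working it through.** The documents give no sample size, power or expected value for this outcome, so there is no stated figure to reproduce. The check is whether correlation responds to a loss of variability.

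**Inputs from the documents:** averaging over three beats (Introduction); 30-minute tracings (Objectives); four-minute intervals (Secondary Outcomes). **Assumed:** the autocorrelation of the beat series, or the size of slow drift relative to beat-to-beat variation. The documents give neither, so ranges are shown.

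**1. Amplitude.** Let x be a tracing's variation about its mean, and let y = 140 + 0.5x. The standard deviation (SD) of y is half that of x, yet r = 1.00. Correlation does not depend on scale.

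**2. Three-beat trailing mean, first-order autoregressive series with lag-1 autocorrelation φ.** Let v = (3 + 4φ + 2φ²)/9. Then:

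- correlation of averaged with raw series: r = [(1 + φ + φ²)/3]/√v
- overall SD ratio, averaged to raw: √v
- SD ratio of beat-to-beat change, averaged to raw: √(1 + φ + φ²)/3

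For φ = 0.9: v = (3 + 3.6 + 1.62)/9 = 0.913, √v = 0.956, and r = 0.903/0.956 = 0.945. The beat-to-beat ratio is √2.71/3 = 0.55.

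| φ (assumed) | r | Overall SD ratio | Beat-to-beat change SD ratio |
|---|---|---|---|
| 0 | 0.577 | 0.577 | 0.33 |
| 0.5 | 0.746 | 0.782 | 0.44 |
| 0.8 | 0.892 | 0.912 | 0.52 |
| 0.9 | 0.945 | 0.956 | 0.55 |
| 0.95 | 0.972 | 0.978 | 0.56 |
| 0.98 | 0.989 | 0.991 | 0.57 |

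Simulation of 4,200 beats (30 minutes at an assumed 140 bpm) agreed with these formulas. With φ of 0.9 or more, r is about 0.95 to 0.99 while beat-to-beat change falls by 43% to 45%. With little autocorrelation, r falls visibly.

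**3. Slow drift (SD D) plus independent beat-to-beat variation (SD s), drift constant over three beats.** Here r = √[(D² + s²/3)/(D² + s²)]. With s = 2 bpm:

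- D = 8: √(65.33/68) = 0.98
- D = 4: √(17.33/20) = 0.93
- D = 2: √(5.33/8) = 0.82
- D = 0: √(1.33/4) = 0.58

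In all four cases the beat-to-beat SD falls by the same 1 − 1/√3 = 42%. One loss of variability therefore gives four different correlations.

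**4. Attribution.** Correlation is symmetric in the two tracings. Take two tracings that share a sinusoidal swing of ±15 bpm (variance 15²/2 = 112.5), with independent short-term SDs of 5 and 1 bpm. Then r = 112.5/√(137.5 × 113.5) = 0.90. The value does not show which tracing is the flatter one, nor does it separate smoothing from noise or misalignment.

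**5. Intervals.** 30/4 = 7.5: seven complete intervals and 2 minutes over, with no rule for the remainder.

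**The case against.** The best defence is that the categories are the real measurement and that correlation is used loosely to mean agreement between tracings. The bullet goes on to classify intervals, compare the classes and name the scalp electrode as the most accurate. Read that way, the outcome is not blind to flattening, because a Doppler shift towards lower classes could appear. This is a sensible reading and it limits the harm. The text does not state it, however, and the sentence framed as the definition says something else.

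Four stronger conclusions are tempting, and the documents do not support them.

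- *Correlation would always hide Doppler smoothing.* The range above runs from visible loss of correlation to almost none. The half-amplitude case shows a property of correlation; it does not describe the Doppler.
- *A flattening device would be declared equivalent.* The plan contains no equivalence rule and no correlation threshold.
- *The study would miss what it was designed to show.* The Purpose section mentions accuracy, but the primary outcomes and all the sample-size reasoning concern continuity of readable tracing. Variability is one of 15 secondary outcomes.
- *Four-minute intervals are an error.* They only need a rule for the remainder. Five-minute intervals would divide 30 evenly but are a preference, and they give six complete intervals instead of seven.

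**Conclusion.** The point holds in limited form. One secondary outcome has two non-equivalent definitions, and the one stated as the definition cannot measure or compare each device's variability. That follows from the wording and from the scale-invariance of correlation, and needs no assumed value.

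The effect on detecting three-beat averaging does rest on assumptions: r is about 0.58 to 0.99 across those tried. The supportable statement is that correlation can hide smoothing and cannot attribute it. Whether the classes would detect it depends on cut-points the plan does not give. In the strongly autocorrelated cases overall SD falls by only 1% to 4%, so a shift in class is possible but not assured.

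The consequence is confined to the reporting of one secondary outcome. No primary outcome or sample size is affected, so the change is desirable and not essential.

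**What to change.** In the Secondary Outcomes bullet:

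1. Delete the sentence defining variability as a correlation. Correlation may stay as a separate descriptive measure of co-movement, with its type and sampling interval stated.
2. Define the outcome as the variability class of each interval of each tracing, with the same stated cut-points for every device.
3. State what happens to the 2 minutes left over from 30 if four-minute intervals are kept.
4. Report agreement by weighted kappa between the EUM and the simultaneously recorded monitor, with confidence intervals that allow for clustering of intervals within woman. Do this separately for women monitored by scalp electrode, where the monitor is the reference, and for women monitored by Doppler, where agreement does not show which device is right.
5. Report the shift in class distribution between the two devices as well. Kappa is also symmetric and does not give the direction of disagreement.
6. Compare Doppler directly with the scalp electrode only if both were recorded in the same woman. The file described holds a single monitor heart rate column, so this contrast may not be available without extra data capture.

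The cost is revised wording and a small amount of extra analysis for one secondary outcome. Items 1 to 5 use the signals already planned, and no sample size changes.
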